### **9.4 Safety and Tolerability Assessments**

#### **9.4.1 Adverse events**

Where changes in severity are recorded in the Case Report Form (CRF), each separate severity of the AE will be reported in the listings, only the most severe will be used in the summary

tables. A pre-existing condition is defined as an AE that starts before the subject has provided written informed consent and is ongoing at consent. A non-treatment emergent AE is defined as an AE which starts after informed consent but prior to dosing. A treatment-emergent AE is defined as an AE which occurs postdose or which is present prior to dosing and becomes more severe postdose. Adverse events by day of onset will be presented.

All AEs will be listed. Treatment-emergent AEs will be summarized by treatment, severity and relationship to the study drug. The frequency (the number of AEs, the number of subjects experiencing an AE and the percentage of subjects experiencing an AE) of treatment-emergent AEs will be summarized by treatment, Medical Dictionary for Regulatory Activities (MedDRA) version 21.0 system organ class and preferred term. The summary and frequency AE tables will be presented for all causalities and those considered related to the study drug. Any serious AEs will be tabulated.

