3.3. Benefit/Risk Assessment

Oral doses of lasmiditan up to the highest single and multiple oral dose given (400 mg) were well tolerated in healthy subjects, with no drug-related serious adverse events (SAEs) or withdrawals due to AEs as of 05 March 2018. Lasmiditan caused no significant QT prolongation either at 100 or 400 mg, and no clinically significant changes in clinical laboratory data. Lasmiditan has been associated with transient lowering of heart rate (on average about 8 to 12 bpm). Throughout this study, vital signs will be closely monitored for effects of lasmiditan on heart rate. Although nervous system disorders were commonly reported as AEs, especially at higher dose levels, they were generally mild or moderate in intensity. Dosing of subjects in this study will be conducted in an inpatient setting, and subjects will be monitored in-house for at least 48 hours after the last dose of investigational product (IP).

There is no anticipated therapeutic benefit for the subjects.

More information about the known and expected benefits, risks, SAEs, and reasonably anticipated AEs of lasmiditan are to be found in the IB.

4. Objectives and Endpoints

Table LAIC.1 shows the objectives and endpoints of the study.

Table LAIC.1. Objectives and Endpoints

Objectives	Endpoints

Primary To evaluate the PK of single and multiple doses of lasmiditan in healthy Chinese subjects.
	AUC(0-∞) [single-dose only], AUC(0-τ), C _{max} , and t _{max} .

Secondary To explore the safety and tolerability of single and multiple oral doses of lasmiditan in healthy Chinese subjects.
	Incidence of SAEs and TEAEs.

Exploratory To evaluate the PK of metabolites M7, M8, (S,R)-M18, and (S,S)-M18 in healthy Chinese subjects.
	AUC(0-∞), C _{max} , and t _{max} .

Abbreviations: AUC(0-∞) = area under the concentration versus time curve from time zero extrapolated to infinity; AUC(0-τ) = area under the concentration versus time curve over a dosing interval; C_{max} = maximum observed plasma concentration; PK = pharmacokinetics; SAE = serious adverse event; TEAE = treatment-emergent adverse event; t_{max} = time of maximum observed plasma concentration.

5. Study Design

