#### **4.2 Secondary objective**

To explore the safety and tolerability of single and multiple oral doses of lasmiditan in healthy Chinese subjects.

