## 9. STATISTICAL METHODOLOGY

### 9.1 General

Data listings will be provided for all data that is databased. Summary statistics and statistical analysis will only be presented for data where detailed in this SAP. For continuous data, summary statistics will include the arithmetic mean, arithmetic standard deviation (SD), median, min, max and N; for log-normal data (e.g. the PK parameters: area under the concentration versus time curves [AUCs] and the maximum observed drug concentration [ $C_{max}$ ]) the geometric mean and geometric coefficient of variation (CV%) will also be presented. For categorical data, frequency count and percentages will be presented. Data listings will be provided for all subjects up to the point of withdrawal, with any subjects excluded from the relevant population highlighted. Summary statistics and statistical analyses will generally only be performed for subjects included in the relevant analysis population. For the calculation of summary statistics and statistical analysis, unrounded data will be used.

Mean change from baseline is the mean of all individual subjects' change from baseline values. Each individual change from baseline will be calculated by subtracting the individual subject's baseline value from the value at the timepoint. The individual subject's change from baseline values will be used to calculate the mean change from baseline using a SAS procedure such as Proc Univariate.

Data analysis will be performed using SAS® Version 9.4 or greater.

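### Does the SAP fall short of the secondary objective by not tabulating treatment-emergent adverse events separately for the single dose and the repeated doses?

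*SAP*

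**What the plan says.** SAP 4.2 states the secondary objective: "To explore the safety and tolerability of single and multiple oral doses of lasmiditan in healthy Chinese subjects". Protocol Section 4 (Table LAIC.1) attaches one endpoint to it: "Incidence of SAEs and TEAEs".

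SAP 9.4.1 plans the following adverse event outputs:

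- A summary: "Treatment-emergent AEs will be summarized by treatment, severity and relationship to the study drug".
- A frequency table giving the number of events and the number and percentage of affected subjects. The frequency "of treatment-emergent AEs will be summarized by treatment, Medical Dictionary for Regulatory Activities (MedDRA) version 21.0 system organ class and preferred term".
- Both tables in two versions: "The summary and frequency AE tables will be presented for all causalities and those considered related to the study drug".
- A display over time: "Adverse events by day of onset will be presented".
- A listing of every event. Where severity changes, "each separate severity of the AE will be reported in the listings, only the most severe will be used in the summary" tables.

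SAP 6 gives four treatment labels for the outputs (placebo, 50, 100 and 200 mg), none divided by phase. SAP 8 defines a single safety population, everyone dosed at least once, with placebo pooled across cohorts. SAP 9.1 adds that "Summary statistics and statistical analysis will only be presented for data where detailed in this SAP".

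**The concern.** Every subject passes through two distinct periods: one dose on Day 1, then a gap of at least 72 hours, then seven daily doses on Days 4 to 10. The objective names both regimens. The pharmacokinetic analysis treats Day 1 and Day 10 separately, and laboratory values and vital signs are summarised by timepoint. The adverse event tables alone merge the whole period into one column per treatment. Read with the restriction in SAP 9.1, this suggests that the report could not say, from a planned table, how many subjects had a TEAE after one dose and how many during repeated dosing.

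The distinction has some clinical interest. Lasmiditan is being developed for acute treatment, and the Phase 3 experience described in Protocol 3.2 comes from patients treating one attack. The single-dose figure is therefore the closest match to that background, and an incidence pooled over eight doses could be well above it.

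**Working it through.** **1. What is required against what is planned.**

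| Requirement | Where | Delivered by |
|---|---|---|
| Incidence of serious and treatment-emergent events, no phase named | Protocol Section 4, Table LAIC.1 | SAP 9.4.1 frequency table; serious events tabulated |
| Incidence for each treatment, by severity and by association with study drug | Protocol 10.3.1.1 | SAP 9.4.1 summary table |
| Pharmacokinetics on Day 1 and on Day 10 | Protocol 10.3.2.2 | SAP 9.3.2, days analysed separately |

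The protocol asks for a split by day for pharmacokinetics and asks for none for adverse events. The SAP carries over both choices, which agrees with its statement in Section 11 that nothing was changed. No stated requirement is missed.

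**2. Does the plan lose the timing?** Doses fall on Day 1 and Days 4 to 10, so day of onset separates the phases except for events starting on Day 4, where onset time is needed. The by-day display alone does not give subjects per phase. Take two constructed data sets, each with 4 affected subjects who all have an event on Day 1, and one further event on each of Days 4, 5, 6 and 7:

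- A: the four later events come from four different subjects, so 4 subjects are affected in the repeated-dose phase.
- B: all four later events come from one subject, so 1 subject is affected.

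Overall and daily counts are identical in A and B. The listings tell them apart, and all events are listed for a study of at most 3 × 12 = 36 subjects. The information is therefore kept.

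**3. What would a phase table show?** Follow-up is 7 to 10 days after the Day 10 dose, which is Day 17 to Day 20.

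- Phase 1: 4 − 1 = 3 days, one dose.
- Phase 2: 17 − 4 = 13 to 20 − 4 = 16 days, seven doses. That is 7 dosing days plus 6 to 9 days off drug.

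The two percentages would cover periods of very different length and could not be compared directly.

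Assume an equal risk p at each dose; the documents give no such figure. If the same subjects react every time, every column equals p. If doses act independently, incidence over k doses is 1 − (1 − p)^k:

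| p | Single dose | Seven doses (phase 2) | Eight doses (overall table) |
|---|---|---|---|
| 5% | 5% | 1 − 0.95^7 = 30% | 1 − 0.95^8 = 34% |
| 10% | 10% | 1 − 0.90^7 = 52% | 1 − 0.90^8 = 57% |
| 20% | 20% | 1 − 0.80^7 = 79% | 1 − 0.80^8 = 83% |

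Under either extreme the phase 2 column stays within 5 percentage points of the overall figure. What a split would add is mainly the single-dose column.

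**4. Precision.** There are 10 subjects per lasmiditan dose and 3 × 2 = 6 on pooled placebo, so one subject is worth 10 or 17 percentage points. Exact 95% intervals are 2.5% to 55.6% for 2/10, 0 to 30.8% for 0/10 and 0 to 45.9% for 0/6.

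**The case for a change.** The best argument for the concern is that the objective says single and multiple, and the overall incidence cannot be converted back into a single-dose incidence. At a 10% risk per dose, the overall figure could be anywhere from 10% to 57%, depending on whether the same subjects react. The SAP does not say whether the by-day display counts events or subjects, or over what denominator, and the example above shows that daily counts cannot be added up. Anyone counting from the listings would have to choose, after seeing the data, how to handle an event that starts before Day 4 and worsens later, or one with no onset time.

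All of this is factually right, and the SAP text does not commit to a per-phase count. It does not amount to an error, for four reasons. First, the counting unit and denominator are layout details, and SAP 3 places the detailed description of outputs in the accompanying shell document, which was not available here. Second, the restriction in SAP 9.1 is not the last word: SAP 3 allows supplementary analyses if they are identified in the report, and Protocol 10.3.1.2 allows further safety analysis if the data warrant it. Third, the late choice of attribution rule affects only a few borderline events. SAP 9.4.8 plans no inference, so no test or error rate depends on it. Fourth, the gap between 10% and 57% shows that one dose differs from eight; it does not show that the overall incidence is wrong as a measure of the named endpoint.

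**Conclusion.** The concern does not hold. The planned tables deliver the endpoint that the protocol names, in the form that Protocol 10.3.1.1 asks for, and the day-of-onset display with the listings keeps what is needed to separate the Day 1 dose from the repeated doses. Separate columns per phase would be a preference about presentation. Leaving them out changes no planned estimate, introduces no bias and alters no conclusion.

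This rests on taking the endpoint in Table LAIC.1 as written, on safety remaining descriptive, and on the listings being produced in full as SAP 9.4.1 states. It does not depend on what the shell document contains: if the shells already split by phase, the question disappears, and if they do not, the plan still meets its stated requirements. The percentages by number of doses rest on assumed risks of 5%, 10% and 20% per dose and serve only as illustration.

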#### **9.4.2 Concomitant medication**

Concomitant medication will be coded using the World Health Organization (WHO) drug dictionary (Version March 2018 Enhanced B2). Concomitant medication will be listed.

#### **9.4.3 Clinical laboratory parameters**

All clinical chemistry and hematology data will be listed and summarized by parameter, treatment, and timepoint together with changes from baseline, where baseline is defined as Day 1, predose. Urinalysis data will be listed. Additionally clinical chemistry, hematology and urinalysis data outside the reference ranges will be listed.

Values for any clinical chemistry, hematology and urinalysis values outside the reference ranges will be flagged on the individual subject data listings.

#### **9.4.4 Vital signs**

Orthostatic vital signs will be calculated as the standing value, minus the last supine value taken prior to the standing value.

Vital signs data will be summarized by treatment and timepoint together with changes from baseline, where baseline is defined as Day 1, predose. Figures of mean vital signs and mean changes from baseline profiles by treatment will be presented.

Furthermore, values for individual subjects will be listed.

#### **9.4.5 Electrocardiogram**

For each subject, ECGs will be performed for safety purposes only, and will not be reported.

#### **9.4.6 Columbia Suicide Severity Rating Scale and Lilly Self-Harm Supplement**

Data from the C-SSRS questionnaire will be listed for individual subjects.

#### **9.4.7 Other assessments**

All other safety assessments not detailed in this section will be listed but not summarized or statistically analyzed.

#### **9.4.8 Safety and Tolerability Statistical Methodology**

No inferential statistical analyses are planned.

### **10. INTERIM ANALYSES**

No interim statistical analyses are planned.

### **11. CHANGES FROM THE PROTOCOL SPECIFIED STATISTICAL ANALYSES**

There were no changes from the protocol specified statistical analyses.

### **13. DATA PRESENTATION**

#### **13.1 Derived Parameters**

Individual derived parameters (e.g. PK parameters) and appropriate summary statistics will be reported to three significant figures. Observed concentration data, e.g.  $C_{max}$ , should be reported as received. Observed time data, e.g.  $t_{max}$ , should be reported as received. N and percentage values should be reported as whole numbers. Median values should be treated as an observed parameter and reported to the same number of decimal places as minimum and maximum values.

#### **13.2 Missing Data**

Missing data will not be displayed in listings.

#### **13.3 Insufficient Data for Presentation**

Some of the TFLs may not have sufficient numbers of subjects or data for presentation. If this occurs, the blank TFL shell will be presented with a message printed in the centre of the table, such as, "No serious adverse events occurred for this study."

Leo Document ID = e249a52e-e5ab-449a-998f-5800f065f1c0

Approver: PPD

Approval Date & Time: 25-Sep-2018 10:35:52 GMT

Signature meaning: Approved

Approver: PPD

Approval Date & Time: 25-Sep-2018 13:44:58 GMT

Signature meaning: Approved

Approver: PPD

Approval Date & Time: 25-Sep-2018 14:19:40 GMT

Signature meaning: Approved

Approver: PPD

Approval Date & Time: 25-Sep-2018 20:18:21 GMT

Signature meaning: Approved
